2.3 Exploratory Efficacy Endpoints

There are no exploratory efficacy endpoints.

2.4 Safety Endpoints

Primary Safety – No evidence of significant in-hospital or 30-day MAEs. No evidence of clinically significant perforation¹, clinically significant embolization or ≥Grade C dissection¹ after Wingman CTO crossing after Wingman CTO crossing and prior to adjunctive interventions, confirmed by angiography.

The components of the composite primary safety endpoint include:

- Major Adverse Events (MAEs) defined as death, unplanned target limb major amputation, and emergent target vessel revascularization.
- Clinically significant perforation defined as all perforations requiring intervention (e.g., covered stent, bypass or other surgery).
- Clinically significant embolization defined as those events that result in distal ischemia (e.g., occlusion of run-off vessel resulting in pain or foot discoloration) and/or requires rescue intervention.
- Grade C Dissection or greater with a minimum of a dissection protruding outside the lumen of the vessel persisting after passage of the contrast material.

The components of the primary safety endpoints will be adjudicated by an independent CEC with angiographic elements assessed by an independent core laboratory.

¹ That occur from study device, as adjudicated by the CEC. This would not include perforations or grade C dissections that occur before the use of the study device or those that occur after use of a commercially available therapeutic device (e.g. from atherectomy)

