2 ENDPOINT DEFINITIONS

2.1 Primary Efficacy Endpoint

Successful CTO Crossing – While using the Wingman device, successful CTO crossing is identified by successful guidewire placement in the distal true lumen confirmed by angiography with no clinically significant perforations.

All of the angiographic films obtained from this study will be reviewed by an independent core lab. Information from their angiographic review will be recorded on CRFs and tabulated for endpoint analysis. Angiographic review will include assessments of: lesions lengths, occlusion lengths, reference vessel diameter, calcification severity, successful CTO crossing, perforation and dissection.

In the event angiographic films are unavailable for assessment by the core lab, site-reported visual assessments will be used for analysis.

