3.1 Intention-To-Treat Population

The subject is enrolled in the study once informed consent has been obtained. If the subject has provided informed consent but has not met one of the criteria for inclusion into the study, they will be considered a screen failure.

Modified Intention to Treat (mITT) Population: The modified intention to treat (mITT) population will include all consented subjects who are exposed to the investigational device. Subjects who give consent but are not exposed to the investigational device or do not undergo the procedure will not be included in this population. The primary study endpoints will be evaluated in the mITT population.

The study visit flow is as follows:

Activity	Visit 1 (Baseline Evaluation) ^a	Visit 2 ^a (Index Procedure through Discharge)	Visit 3 (Follow-Up Evaluation) ^e
Eligibility Screening	X		
Informed Consent	X		
History and Physical Examination of target limb ^f	X		
Vital Signs ^b	X	X	
Ankle-Brachial or Toe-Brachial and Rutherford Assessments	X	X	X
Medication History and Review	X		
Peripheral Arterial Disease/CTO Confirmation ^c	X		
Laboratory Tests ^d	X		
Interventional Procedure and Angiography		X	
Adverse Experience Assessment		X	X
Device Accountability		X	
Protocol Deviations	X	X	X

^a Visit 1 and Visit 2 study procedures may be conducted during one study visit, permitting that Visit 1 procedures have been performed within the past 90 days and are completed prior to the start of the interventional procedure. Urine pregnancy tests will also be conducted as necessary during the baseline evaluation per local requirements.

^b Blood pressure, heart rate, respiratory rate, and weight.

^c Confirmation of an occluded artery ≥ 2.0 mm in diameter requiring intervention based on contrast, CT or MR angiography.

^d As per pre-interventional catheterization laboratory standard procedures.

Statistical Analysis Plan

^e Visit will occur 30 days (+/- 7 days) post-interventional procedure.

^f Existence of gangrene, tissue deficit, blue toe syndrome or any evidence of acute ischemia in low limb.

Missing data will not be imputed. However, a tipping point sensitivity analysis on the primary endpoints will be done.

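### The primary safety window opens after Wingman crossing, which conflicts with footnote 1 for perforation and dissection and leaves embolization in failed attempts outside the endpoint as written

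*SAP*

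**What the plan says.** SAP 2.4 has two parts to the primary safety endpoint. The MAE part (death, unplanned target limb major amputation, emergent target vessel revascularization) reads "No evidence of significant in-hospital or 30-day MAEs" and is not tied to crossing. The angiographic part covers perforation, embolization and dissection, and looks for them "after Wingman CTO crossing and prior to adjunctive interventions, confirmed by angiography". The Protocol Summary uses the same window. The SAP sentence also repeats its opening phrase, which is a plain editing slip.

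Footnote 1 to SAP 2.4 is marked on perforation and on dissection, not on embolization. It limits events to those "That occur from study device, as adjudicated by the CEC" and continues: "This would not include perforations or grade C dissections that occur before the use of the study device". It also leaves out those that follow use of a commercial therapeutic device. The component list adds "Clinically significant perforation defined as all perforations requiring intervention".

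SAP 3.1 defines the mITT set: the "population will include all consented subjects who are exposed to the investigational device". It then states: "The primary study endpoints will be evaluated in the mITT population". Neither document says how the three angiographic components are counted when the Wingman fails to cross.

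**The concern.** A failed attempt never reaches the point at which the window opens. Under the literal wording, a device-caused perforation, dissection or embolization in such a subject is not an event unless it also leads to an MAE. The subject still counts in the denominator, as event-free. A Grade C dissection that leads to no death, major amputation or emergent revascularization is an example of what would be lost.

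The comparison is single-arm against a fixed goal, so no control group shares the omission. Any event left out moves the result in the device's favour. The CEC and core laboratory also have two possible start points for perforation and dissection, which leaves failed cases to discretion.

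**Working it through.** **1. The start point, component by component**

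| Component | Main sentence, SAP 2.4 | Footnote 1, SAP 2.4 | Failed attempts |
|---|---|---|---|
| Perforation | after crossing | from use of the study device | sentence and footnote conflict |
| Grade C or greater dissection | after crossing | from use of the study device | sentence and footnote conflict |
| Embolization | after crossing | not attached | not included by any text |
| MAE | in hospital or to 30 days | not attached | included |

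The footnote's start is an inference. If counting began only at a completed crossing, there would be no need to exclude events that precede use of the device.

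**2. The plan's own figures**

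Inputs from SAP 1.4 and 4.3: goal 13.0%, assumed rate 5.0%, one-sided alpha 0.05, effective N 80, total 85, assumed crossing success 83.2%. SAP 1.4 names the exact binomial for sample size; I take the confidence limit in 4.3 to be exact as well.

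- Exact one-sided 95% upper limits at n=80: 5 events give 12.69%, 6 give 14.27%. At n=85: 11.97% and 13.46%. The test passes with at most 5 events at either size.
- Safety at n=80: P(X ≤ 5) is 4.3% at 13.0% (type I error) and 78.9% at 5.0% (power), about one point under the stated 80%.
- Efficacy at n=80: at least 64 crossings needed, power 82.2%.
- Enrolment: 80 / 0.95 = 84.2, rounded up to 85.

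**3. Effect on the false-pass chance under the literal reading**

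Assumptions: 1 − 0.832 = 16.8% are not crossed (80 × 0.168 = 13.4 subjects; 85 × 0.168 = 14.3); every event is angiographic; every event in a non-crosser is lost; risk is equal in crossers and non-crossers.

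Counted rate = 0.130 × (1 − 0.168) = 10.8%.

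| n | P(X ≤ 5) at 13.0% | P(X ≤ 5) at 10.8% |
|---|---|---|
| 80 | 4.3% | 12.4% |
| 85 | 2.8% | 9.2% |

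The result depends on the share of events lost. At n=80 it is 8.2% if 10% of events are lost and 25.4% if 30% are.

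**4. Effect on the reported rate**

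Let q be the event rate in non-crossers (not in the documents; the range is an assumption) and 5% the rate in crossers. Counted rate = 0.832 × 5% = 4.2%. Understatement = 0.168 × q.

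| q | Understatement (points) | Full rate | Chance of passing at n=80, all events counted |
|---|---|---|---|
| 5% | 0.8 | 5.0% | 79% |
| 10% | 1.7 | 5.8% | 68% |
| 20% | 3.4 | 7.5% | 44% |
| 30% | 5.0 | 9.2% | 24% |

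With the events in non-crossers left out, the chance of passing is 88% in every row.

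**The case against.** The best defence is that the phrase fixes when evidence is looked for, not when the injury must occur: on the angiogram after the Wingman step and before other treatment. This stands for completed crossings. A reader might infer that injuries made during a successful crossing fall outside the window, but a perforation or dissection made then is still evident on that angiogram. The documents do not support that inference.

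The footnote is also a fair answer for perforation and dissection, since it points to use of the device as the start. It shows likely intent, but it does not amend the sentence it annotates, and it does not reach embolization. The mITT rule keeps non-crossers in the analysis without making their injuries count. The phrase about all perforations requiring intervention sets severity, not timing.

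A reader might also import SAP 2.1, where success means "successful guidewire placement in the distal true lumen confirmed by angiography with no clinically significant perforations", and conclude that a perforated case can never have crossed. That goes too far. SAP 2.4 speaks of crossing without requiring success, and the import would empty a component that the endpoint names.

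The size is open to challenge too. The 16.8% is the complement of a literature rate. Under SAP 2.1, failures can include vessels that were crossed with a perforation, so the share with no crossing may be smaller. MAEs in non-crossers still count, which also lowers the effect.

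**Conclusion.** The point holds as a contradiction and a gap in the definition of the primary safety endpoint. For perforation and dissection, the sentence and its footnote give different start points. For embolization, no text covers a failed attempt.

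The direction is certain: any omission favours the device, and with at most 5 events allowed, one can decide the outcome. The size is not known. The rise to 12.4% (n=80) or 9.2% (n=85) is an upper bound at equal risk, resting on the literal reading and the assumptions in step 3; a higher risk in failed attempts would raise it. If adjudicators follow the footnote, only embolization is affected, and the documents give no separate rate for it.

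A reader might infer that the safety rate is shown to be understated. It is not: the documents do not establish that adjudicators will apply the literal reading, and they give no event rate in non-crossers.

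**What to change.** In SAP 2.4 and the protocol, define one window for all three angiographic components. It runs from first introduction of the Wingman, whether or not it crosses, until first use of another crossing device or an adjunctive therapeutic device, or the end of the procedure if neither is used. Closing it at another crossing device keeps that device's injuries from being charged to the Wingman.

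Extend the attribution rule of footnote 1 (study device as cause, decided by the CEC) to embolization. State that every mITT subject is assessed for all three components. Remove the repeated phrase.

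The cost is wording, with matching instructions to the CEC and core laboratory. SAP 2.1 already sends all films to the core laboratory, though its list of assessments does not name embolization, which should be added. The planned sample size does not change. Any failed attempts already adjudicated would need a second look under the new rule. The reported safety rate may be slightly less favourable. If failed attempts were always meant to count, the change only records that.

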3 ANALYSIS POPULATIONS

Statistical Analysis Plan

3.1 Intention-To-Treat Population

The subject is enrolled in the study once informed consent has been obtained. If the subject has provided informed consent but has not met one of the criteria for inclusion into the study, they will be considered a screen failure.

Modified Intention to Treat (mITT) Population: The modified intention to treat (mITT) population will include all consented subjects who are exposed to the investigational device. Subjects who give consent but are not exposed to the investigational device or do not undergo the procedure will not be included in this population. The primary study endpoints will be evaluated in the mITT population.

The study visit flow is as follows:

Activity	Visit 1 (Baseline Evaluation) ^a	Visit 2 ^a (Index Procedure through Discharge)	Visit 3 (Follow-Up Evaluation) ^e
Eligibility Screening	X		
Informed Consent	X		
History and Physical Examination of target limb ^f	X		
Vital Signs ^b	X	X	
Ankle-Brachial or Toe-Brachial and Rutherford Assessments	X	X	X
Medication History and Review	X		
Peripheral Arterial Disease/CTO Confirmation ^c	X		
Laboratory Tests ^d	X		
Interventional Procedure and Angiography		X	
Adverse Experience Assessment		X	X
Device Accountability		X	
Protocol Deviations	X	X	X

^a Visit 1 and Visit 2 study procedures may be conducted during one study visit, permitting that Visit 1 procedures have been performed within the past 90 days and are completed prior to the start of the interventional procedure. Urine pregnancy tests will also be conducted as necessary during the baseline evaluation per local requirements.

^b Blood pressure, heart rate, respiratory rate, and weight.

^c Confirmation of an occluded artery ≥ 2.0 mm in diameter requiring intervention based on contrast, CT or MR angiography.

^d As per pre-interventional catheterization laboratory standard procedures.

Statistical Analysis Plan

^e Visit will occur 30 days (+/- 7 days) post-interventional procedure.

^f Existence of gangrene, tissue deficit, blue toe syndrome or any evidence of acute ischemia in low limb.

Missing data will not be imputed. However, a tipping point sensitivity analysis on the primary endpoints will be done.

3.2 Per Protocol Population

The per protocol population will include all enrolled subjects that meet the eligibility criteria, are exposed to the investigational device, undergo the index procedure and complete the 30-day follow up visit.

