Reflow Medical Wingman Catheter Wing-IT Clinical Trial
RFM-CTO-13001
NCT03403426
Document Date: 03-OCT-2018

PROTOCOL SUMMARY

- Title:** A Non-Randomized Study Evaluating the Use of the ReFlow Medical **Wingman** Catheter to Cross Chronic Total Occlusions in Infringuinal Peripheral ArTeries (Wing-IT)
- Design:** Prospective, multi-center, non-randomized single-arm study of the Wingman Catheter to cross a single infringuinal peripheral chronic total occlusion (CTO). Safety and effectiveness will be evaluated during the index procedure through 30-day follow-up.
- Purpose:** To evaluate the safety and effectiveness of the ReFlow Medical Wingman Catheter used to cross *de novo* or restenotic infringuinal CTOs that cannot be crossed with a standard guidewire.
- Enrollment and Sites:** A maximum of 85 patients will be enrolled and treated with the investigational device at up to twelve (12) centers in North America and three (3) centers in Europe.
- Time Course:** Initial enrollment: Q1 2018
Last enrollment: Q1 2019
Last follow-up: Q1 2019
- Primary Efficacy and Safety Endpoints:** Primary Efficacy:
While using the Wingman device, successful CTO crossing is identified by successful guidewire placement in the distal true lumen confirmed by angiography with no clinically significant perforations.
Primary Safety:
No evidence of significant in-hospital or 30-day MAEs. No evidence of clinically significant perforation, clinically significant embolization or \geq Grade C dissection, after Wingman CTO crossing and prior to adjunctive interventions, confirmed by angiography. Components of the composite primary safety endpoint include:
- Major Adverse Events (MAEs) defined as death, unplanned target limb major amputation, and emergent target vessel revascularization.
 - Clinically significant perforation defined as all perforations requiring intervention (e.g., covered stent, bypass or other surgery)¹
 - Clinically significant embolization defined as those events that result in distal ischemia (e.g., occlusion of run-off vessel

resulting in pain or foot discoloration) and/or requires rescue intervention.

- Grade C Dissection or greater with a minimum of a dissection protruding outside the lumen of the vessel persisting after passage of the contrast material.¹

The components of the primary and secondary safety endpoints will be adjudicated by an independent CEC with angiographic elements assessed by an independent core laboratory.

Secondary Endpoints:

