1.4 Sample Size Considerations

The exact binomial distribution is used for calculation of the sample size. The hypotheses and sample size calculations provided in the clinical study protocol are as follows.

The null and alternative hypotheses of the primary efficacy endpoint are:

$$H_0: \pi_{\text{Wingman_efficacy}} \leq \pi_{\text{PG_efficacy}} - \delta_{\text{efficacy}}$$

$$H_A: \pi_{\text{Wingman_efficacy}} > \pi_{\text{PG_efficacy}} - \delta_{\text{efficacy}}$$

where,

$$\pi_{\text{PG_efficacy}} = \text{PG success rate}$$

$$\pi_{\text{Wingman_efficacy}} = \text{Wingman device success rate}$$

Literature Review¹⁻¹¹ indicates that the average success rate of several CTO catheter device types is 83.2%. Using this rate as the historical control and using a non-inferiority margin (δ_{efficacy}) of 12.5% the hypotheses of the primary efficacy endpoint can be rewritten as:

$$H_0: \pi_{\text{Wingman_efficacy}} \leq 70.7\%$$

$$H_A: \pi_{\text{Wingman_efficacy}} > 70.7\%$$

The null and alternative hypotheses of the safety endpoint are:

$$H_0: \pi_{\text{Wingman_safety}} \geq \pi_{\text{PG_safety}} + \delta_{\text{safety}}$$

Statistical Analysis Plan

$$H_A: \pi_{\text{Wingman_safety}} < \pi_{\text{PG_safety}} + \delta_{\text{safety}}$$

where,

$$\pi_{\text{PG_safety}} = \text{PG major adverse event rate}$$

$$\pi_{\text{Wingman_safety}} = \text{Wingman device major adverse event rate}$$

Literature Review¹⁻¹¹ indicates that the average rate of major adverse events, perforations, grade C or higher dissections and embolizations is 5.0%. Using this rate as the historical control, and using a delta of non-inferiority margin (δ_{safety}) 8% for the safety endpoints, the hypotheses can be rewritten as:

$$H_0: \pi_{\text{Wingman_safety}} \geq 13.0\%$$

$$H_A: \pi_{\text{Wingman_safety}} < 13.0\%$$

Assume that the Wingman device has the same success rate and the major adverse event rate as the historical control and further assume that the one-sided type I error rates for the efficacy and safety endpoints are both 0.05. An effective sample size of 80 subjects is needed achieve a power of at least 80% for the efficacy and safety endpoints. To account for a loss of follow up rate of approximately 5%, total enrollment of 85 subjects is required.

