2.2 Secondary Efficacy Endpoints

Statistical Analysis Plan

- Lesion success, defined as attainment of <50% final residual stenosis of the target lesion using any percutaneous method.
- Procedure success, defined as device success and the absence of in-hospital MAEs, clinically significant perforation, clinically significant embolization or Grade C or greater dissection not resolved by visual estimate.
- Evaluation of total procedural and fluoroscopic time and contrast volume.
- Evaluation of procedure time associated with use of the investigational device.
- Evaluation of utility of ancillary device in addition to investigational device.

The angiographic elements of secondary efficacy endpoints will be assessed by an independent core laboratory and the MAE elements adjudicated by an independent CEC. In the event angiographic films are unavailable for assessment by the core lab, site-reported visual assessment will be used for analysis.

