3.3 Safety Population

The safety population is the same as the mITT population for this study.

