4.2 Efficacy Analyses

Statistical Analysis Plan

Descriptive statistics of the primary efficacy endpoint (total number of CTOs, number and percentage of successful CTO crossings, one-sided 95% CI of the percentage) will be presented. The lower bound of the one-sided 95% CI will be compared to the performance goal of 70.7%.

Summary statistics will be presented for procedural and fluoroscopic time and contrast volume and other secondary endpoints. The summary will include number, mean, standard deviation, median, minimum, maximum, as well as the two-sided 95% CI of the mean and box plots for non-normally distributed data.

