4.3 Safety Analyses

Number and percentage of in-hospital and 30-day major adverse event and the one-sided 95% CI will be presented. The upper bound of the one-sided 95% CI will be compared to the performance goal of 13.0%.

Number and percentage of subjects having 30-day MAEs, device successes, lesion successes, procedure successes and subjects having clinically significant perforation, and the corresponding two-sided 95% CIs will be presented.

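### Does the unused per-protocol population leave the denominator of the secondary efficacy endpoints open?

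*SAP*

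**What the plan says.** SAP section 3 defines three populations, two of them identical. The mITT population is every consented subject exposed to the device, and section 3.1 assigns it: "The primary study endpoints will be evaluated in the mITT population". Section 3.3 adds: "The safety population is the same as the mITT population for this study". The PP population of section 3.2 takes eligible subjects who "are exposed to the investigational device, undergo the index procedure and complete the 30-day follow up visit". Apart from that definition, PP appears only in the contents list and the abbreviations.

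The secondary efficacy endpoints are defined in section 2.2 and summarised in two places. Section 4.2 states: "Summary statistics will be presented for procedural and fluoroscopic time and contrast volume and other secondary endpoints". Section 4.3, under Safety Analyses, plans two-sided 95% confidence intervals for "Number and percentage of subjects having 30-day MAEs, device successes, lesion successes, procedure successes and subjects having clinically significant perforation". Neither section names a population. Section 5 leaves the detailed description of the tables to a separate mock document, which is not among the papers reviewed.

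**The concern.** Only the primary endpoints are expressly tied to mITT. A reader who finds a second, narrower population defined and never used may ask whether it was meant for the secondary endpoints.

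PP would suit them poorly. Procedure times, contrast volume, ancillary device use and final residual stenosis are known when the procedure ends. The MAE part of procedure success stops at discharge: "Procedure success, defined as device success and the absence of in-hospital MAEs, clinically significant perforation". A 30-day visit requirement could therefore only discard outcomes already recorded. Some of that loss would run one way: an in-hospital death is a procedure failure, and that subject can never complete the visit.

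Timing adds to the unease. The SAP is dated 20 May 2019, and the Protocol Summary gives "Last follow-up: Q1 2019". If that schedule held, the denominator in a single-arm study could be chosen with the outcomes in view. At stake would be the reported lesion and procedure success rates and their intervals.

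**Working it through.** **Which denominator the text supports**

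| Analysis | Where planned | Population |
|---|---|---|
| Primary efficacy and safety | 4.2, 4.3 | mITT, named in 3.1 |
| Device, lesion and procedure success, with two-sided 95% CI | 4.3, Safety Analyses | Not named; safety population = mITT by 3.3 |
| Times, contrast volume, other secondary summaries | 4.2 | Not named |
| Any PP analysis | None | None |

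Section 4.3 lists the success rates in one sentence with 30-day MAEs and clinically significant perforation, under a single count of subjects. Reading that sentence with two denominators would be forced. The only items without a contextual pointer are the descriptive summaries in section 4.2.

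**Size if PP were used anyway**

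Inputs from SAP section 1.4: 80 effective subjects, about 5% loss, 85 enrolled, and a literature device success rate of 83.2%.

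1. The plan's own figure: 80 / (1 − 0.05) = 84.2, rounded up to 85. This agrees with "To account for a loss of follow up rate of approximately 5%, total enrollment of 85 subjects is required". The allowance is 85 − 80 = 5 subjects.
2. The documents give no assumed lesion or procedure success rate, so 83.2% is borrowed as an assumption: 0.832 × 85 = 70.7, taken as 71 successes and 14 failures. All 85 are assumed exposed and otherwise eligible.
3. Rates with exact (Clopper-Pearson) two-sided 95% intervals where shown:

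| Case | Rate | 95% CI |
|---|---|---|
| mITT | 71/85 = 83.5% | 73.9 to 90.7 |
| PP, all five lost were successes | (71 − 5)/80 = 66/80 = 82.5% | 72.4 to 90.1 |
| PP, all five lost were failures | 71/80 = 88.8% | 79.7 to 94.7 |
| PP, loss unrelated to outcome | 67/80 = 83.8% | – |

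4. The last row: the expected number of failures among five is 5 × 14/85 = 0.8, so about one failure and four successes are lost, and 71 − 4 = 67.
5. Against mITT the extremes are 82.5 − 83.5 = −1.0 point and 88.75 − 83.53 = +5.2 points.
6. With two non-completers the extremes narrow to 69/83 = 83.1% and 71/83 = 85.5%.
7. The one mechanism with a sure direction, an in-hospital death, moves the rate from 71/85 = 83.5% to 71/84 = 84.5%, about 1 point per death. The documents give no count of such deaths.

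**The case for a change.** The strongest case for a change is that section 3 exists to settle populations in advance, and it settles only the primary endpoints. That mITT covers the rest is an inference from a section title, and the inference does not reach the times and contrast volume in section 4.2. The mock tables may settle the matter, but they cannot be seen here. The tipping point analysis in section 4.6 covers only the primary endpoints. One sentence would remove all doubt at almost no cost.

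The factual part stands: the SAP text does not name the population, and PP has no stated use. PP also applies the eligibility criteria, so it could remove more than the five subjects counted above; the documents give no number.

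The conclusion drawn from this does not stand. A population defined but given no table is surplus wording, not a rival analysis. The timing argument rests on a planned date, and the actual last follow-up is not in the documents. The 5.2-point shift needs every non-completer to be a failure, and nothing in the documents links loss to failure.

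**Conclusion.** No change to the plan is needed. This is missing detail that an analyst fills sensibly: read as written, sections 3.3 and 4.3 together give mITT for the lesion and procedure success rates, and mITT keeps every exposed subject, early deaths included. The descriptive summaries in section 4.2 would follow the same population, since no PP output is planned.

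No decision turns on the point. The hypotheses in section 1.4 and the comparisons with 70.7% and 13.0% concern the primary endpoints, which section 3.1 assigns to mITT. The secondary endpoints have no performance goal.

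Even if PP were used, the rate would stay close to the mITT rate when loss is unrelated to outcome (83.8% against 83.5%). The range of 82.5% to 88.8% marks the limits for five non-completers. These figures assume 85 exposed subjects, a success rate borrowed from the device literature figure, and no exclusions for eligibility. A sentence naming mITT for the secondary endpoints would be editorial and would alter no planned result.
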